2.2 Subjects and Sites

We will work with [name] team and select Mental Health Institute of Second Xiangya Hospital that has approved for carrying out CNS drug registration trial by China Food and Drug Administration and well experienced in doing the MDD trial in China. A total of 120 patients with MDD will be enrolled and randomly divided into 2 groups. Sixty subjects will be given fish oil and another 60 subjects given placebo (control group). We plan to enroll all 120 patients in 12 months and each patient will be on study medication (or placebo) for 24 weeks and then be followed up for after 24 weeks (the follow-up period will be last for 48 weeks). We plan to have this trial done in two year period.

Participants

Inclusion criteria:

- ① Able to provide informed consent;
- ② Men or women aged 18-50 years;
- ③ A primary psychiatric diagnosis of major depressive disorder (MDD), by Diagnostic and Statistical Manual-5th ed (DSM-5) using the MINI;
- ④ HAMD total score ≥ 21 ;
- ⑤ No significantly modification of their diet from the time they sign consent to the end of study participation.

Exclusion criteria:

- ① Suffering from other serious somatic diseases or comorbidities;

- ②Patients with serious nervous system disease;
- ③Patients in accordance with diagnostic standards of other mental illness;
- ④ Patients who need to take benzodiazepine every day, and who currently need to be treated by electroconvulsive therapy or have received electroconvulsive therapy in the past 6 months;
- ⑤Pregnant women or lactating women, women with pregnancy plans during the trial period (12 months), women with a high risk of pregnancy but without taking any contraceptive measures;
- ⑥Patients with apparent suicide attempt or suicidal behavior;
- ⑦ Any condition or medicines that may have an effect on biomarkers (within 1 week of the screening period or during whole trial period): long-term, regular use of NSAIDs, COX-2 inhibitors, immunosuppressant, steroids, interferon, chemotherapeutics, anticoagulants, malignancy, active autoimmune diseases, inflammatory bowel diseases, etc;
- ⑧Allergy history of PUFA;
- ⑨Intake of Fish oil more than 3g per day or eat fatty fish more than 3 times a week.

2.3 Intervention Medications

The experimental group will be given 4 fish oil capsules (1g/one capsule) twice daily after two meals at roughly the same time each day, and lasting for the first 6 months. Fish oil capsule will be provided by the Hunan Kangqi100 Biological Technology Co.Ltd.

The control group will be given 4 soybean oil capsules (placebo capsule,1g/one capsule) twice daily after two meals at roughly the same time each day, and lasting for the first 6 months too. Placebo capsule will also be provided by the Hunan Kangqi100 Biological Technology Co.Ltd. The placebo capsule's appearance and flavor are made the exactly the same as the fish oil capsules.

Study duration: 48 weeks.

2.4 Assessment

Following consent, patients met enrollment criteria to be in the study will be undergone assessments including:

- ① Demographic information, medical and psychiatric history and family history of mental illnesses at baseline;
- ②Labs: CBC, metabolic panel, liver panel and lipid panel (extra sample will be saved for biomarkers);

- ③Clinical symptom will be assessed by HAMD;
- ④Cognitive assessment by RBANS and STROOP;
- ⑤Side effect rated on UKU and Lab tests.

Almost all clinical assessments will be done at baseline, week 4, week 8, week 12, week 24 and week 48, except some items being done at baseline only (See table 1 for details).

For the lab work, in addition to routine clinical safety lab, some extra blood sample will be collected and stored for future epigenetic and bio-inflammatory biomarkers assay.

Table 1: Schedule of Clinical, Neurocognitive Assessment and Lab testing for Evaluation of fish oil add-on therapy in MDD

	Baseline	W04	W08	W12	W24	W 48
Inform consent	*					
Inclusion/exclusion screen	*					
Demographic & medical, mental illness history	*					
Physical exam	*	*	*	*	*	*
Lab test and blood sample stored	*	*		*	*	*
Randomization	*					
Study medication dispense	*	*	*	*		
HAMD, HAMA, CGI, BDI, SAS, RBANS, STROOP, ASEX, Somatic Self-rating Scale	*	*	*	*	*	*
CTQ, SSRS	*					
UKU		*	*	*	*	*
BMD	*				*	*
MRI	*				*	*

3 Overall Approach to Statistical Analysis

Data will be examined for obvious outliers, distribution irregularities, and range errors and processed accordingly. Prior to analyses, the validity of assumptions (e.g., about distributions) will be confirmed. Transformations will be made or a nonparametric procedure may be utilized as needed. Means, standard deviations, ranges or interquartile ranges, and rates of primary outcomes will be reported. Baseline demographics and characteristics will be compared among study groups using F-tests or chi-square tests

or nonparametric equivalents as needed. Baseline variables with significant group differences will be treated as potential confounder variables and will be statistically adjusted for in analyses. Unless stated otherwise, two-sided testing and a 5% level of significance are planned for all statistical tests.

The primary outcome measures will be the clinical symptoms Changes in Hamilton Depression Scale HAMD 6 weeks at week 0, week 4, week 12, week 24 and week 48 among study groups. Secondary outcome measures the Changes in Clinical Global Impression (CGI), Hamilton Anxiety Scale (HAMA), Beck Depression Rating Scale (BDI) and Self-Rating Anxiety Scale (SAS) at week 0, week 4, week 12, week 24 and week 48. And time to relapse for the maintenance phase of the study among study groups.

For hypothesis: Subjects who are randomized to the fish oil will have reduced clinical symptoms and perform better in cognition and improve metabolic markers; inflammation markers than those who are randomized to placebos.

Analyses: After transformation (if necessary to insure the improvement is linear), the difference in the rate of HAMD improvement of fish oil group will be compared with that of the placebo group and the linear mixed effects models will be performed using subjects as the random effect (i.e. the drug-time interaction, with adjustment for baseline values). Secondary analyses will include using GLM to test if treatment arms show effect on CGI, HAMA, BDI, SAS, and other psychological variables. We will also evaluate possible cofounders as well as improvement of neurocognitive domains score and CGI.

4 Key investigator list

Principal Investigator (PI)

[name]. M.D.

Chief Clinical Professor

Mental Health Institute

Second Xiangya Hospital of Central South University

[name]

[contact]

E-mail: [contact], or [contact]

[name]. M.D. (Co-PI)

Department of Pharmacy Xiangya Hospital, Central South University

[name]

[contact]

E-mail: [contact]

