Protocol

Safety, Effectiveness, and Mechanism of Fish Oil as Adjunct Treatment for Major Depressive Disorder - a 12-month Randomized, Placebo Controlled Clinical Trial

Unique Protocol ID: MDD201610

Version number: 0001

Date: October 9, 2016

Second Xiangya Hospital of Central South University

Brief Summary

Unique Protocol ID	MDD201610
Official Title	Safety, Effectiveness, and Mechanism of Fish Oil as Adjunct Treatment for Major Depressive Disorder - a 12-month Randomized, Placebo Controlled Clinical Trial
Version number/Date	0001/October 9, 2016
Sponsor	Second Xiangya Hospital of Central South University
Indication	Major Depressive Disorder
Aim	To investigate the role of n-3 polyunsaturated fatty acids in the treatment of depression.
Study Design	Randomized, double-blind, placebo-controlled Clinical Trial
Number of cases	Experimental Group:60, Placebo Group:60
Number of research centers	2
Estimated Primary Completion Date	October, 2019
Study Arms	Placebo Comparator: Placebo (Soybean oil placebo capsules, 8 capsules daily for 24 weeks) Experimental: Fish oil (fish oil capsules, 8 capsules(containing EPA 1440mg, DHA 960mg) daily for 24 weeks)
Outcome Measures	Primary Outcome Measures: HAM-D ₂₄ , HAMA, BDI, SAS Secondary Outcome Measures: CGI-S, CGI-I, SERS, RBANS, STROOP, BMD, MRI
statistical analysis	SPSS

Safety, Effectiveness, and Mechanism of Fish Oil as Adjunct Treatment for Major Depressive Disorder - a 12-month Randomized, Placebo Controlled Clinical Trial

In this proposed study, we will evaluate the effects of fish oil add-on in treatment of major depressive disorder (MDD). Patients are randomly assigned to two groups (n=60): control group (placebo, soybean), fish oil group (fish oil capsules containing about EPA 1440mg, DHA 960mg). The experimental group will be compared to placebo group to evaluate if it may benefit clinical symptoms, cognitive symptoms and metabolic markers in depressive patients. We also plan to investigate the changes in markers of inflammation at the same time. The study will be carried out in the Second Xiangya Hospital of Central South University in China and recruit 120 depressive patients. Only outpatients will be recruited and the enrolled patients will be assessed (baseline). Eligible participants will be between the ages of 18-60. Subjects will be assessed at baseline, week 4, week 8, week 12, week 24 and week 48.

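### The GLMs for CGI, HAMA, BDI and SAS name no baseline covariate, and the only stated way to add one is a significance test between randomised arms

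*Combined protocol and SAP*

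**What the plan says.** Section 3 (Overall Approach to Statistical Analysis) first sets up baseline testing: "Baseline demographics and characteristics will be compared among study groups using F-tests or chi-square tests", or nonparametric equivalents. It then gives the consequence: "Baseline variables with significant group differences will be treated as potential confounder variables and will be statistically adjusted for in analyses". All tests are two-sided at 5%.

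The Analyses paragraph of the same section gives the HAMD linear mixed model an unconditional baseline term: "the drug-time interaction, with adjustment for baseline values". The next sentence turns to the other scales and names no covariate: "Secondary analyses will include using GLM to test if treatment arms show effect on CGI, HAMA, BDI, SAS, and other psychological variables". The paragraph closes with "We will also evaluate possible cofounders as well as improvement of neurocognitive domains score and CGI", which gives neither a variable nor a criterion.

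These outcomes are defined as changes: "Secondary outcome measures the Changes in Clinical Global Impression (CGI" and so on through HAMA, BDI and SAS. Table 1 in section 2.4 schedules the row "HAMD, HAMA, CGI, BDI, SAS, RBANS, STROOP, ASEX, Somatic Self-rating Scale" at baseline and at every later visit.

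The tier of these scales is unsettled. The Brief Summary lists HAMA, BDI and SAS as primary, and section 3 lists them as secondary.

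**The concern.** Under randomisation, any baseline difference between the arms is due to chance. Testing it answers a question whose answer is already known, and the p-value says nothing about whether the variable predicts outcome. Prognostic strength is what determines how much precision a covariate brings. A rule based on imbalance therefore omits a strong predictor in most trials and admits an irrelevant variable just as often.

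For the four named scales this is the only stated criterion. It is also unclear whether baseline scale scores count among the characteristics to be tested. If they do not, no stated rule brings them into the GLMs at all.

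Baseline is not ignored, because a change score subtracts it. Subtraction fixes the baseline slope at 1, however, where a covariate would let the data estimate it. What is at stake is precision on these scales and a model specified in advance. If HAMA, BDI and SAS are primary, the point matters more.

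**Working it through.** The documents state no power, effect size, SD, dropout rate or baseline-to-outcome correlation, so there is no planned figure to reproduce.

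**Inputs from the documents.** 60 per arm (section 2.2); two-sided 5% (section 3); change-score outcomes (section 3); baseline values collected (Table 1).

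**Assumptions for illustration.** One follow-up visit, normal data, effect d = 0.3, 0.4 or 0.5 follow-up SD, correlation r = 0.3, 0.5 or 0.7, and complete data with equal SDs unless stated.

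**1. When the rule admits a baseline score.** The observed difference must exceed t(0.975, 118) × √(2/60) = 0.3615 SD. By construction this happens in about 5% of randomised trials (simulated: 4.9% to 5.1%), whatever the value of r. If several independent variables are tested, at least one is admitted with probability 1 − 0.95^k: 0.19 for k = 4, 0.40 for k = 10 and 0.64 for k = 20. The covariate set is thus left to chance.

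**2. Precision, independent of effect size.** The residual variance is 2(1 − r) for a change score and 1 − r² with baseline as a covariate. The ratio is (1 − r²)/[2(1 − r)] = (1 + r)/2:

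| r | Variance ratio | 60 per arm has the precision of |
|---|---|---|
| 0.3 | 0.65 | 60/0.65 = 92 |
| 0.5 | 0.75 | 60/0.75 = 80 |
| 0.7 | 0.85 | 60/0.85 = 71 |

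**3. Power.** This was simulated with 100,000 trials per setting. Under the rule, the analysis adjusts for baseline if the baseline test has p < 0.05 and otherwise applies a t-test to the change score. The comparator always adjusts.

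| Setting | Rule, r = 0.3 / 0.5 / 0.7 | Always adjusted | Gain (points) |
|---|---|---|---|
| d = 0.5, 60 per arm | 64.3 / 78.5 / 94.4% | 80.9 / 87.8 / 96.7% | 16.6 / 9.3 / 2.3 |
| d = 0.4, 60 per arm | 45.7 / 59.3 / 80.6% | 62.0 / 70.5 / 85.7% | 16.3 / 11.2 / 5.1 |
| d = 0.3, 60 per arm | 28.0 / 37.0 / 55.9% | 39.8 / 46.5 / 62.3% | 11.8 / 9.5 / 6.4 |
| d = 0.5, 48 per arm (assumed 20% loss) | 54.4 / 68.6 / 88.5% | 71.5 / 79.5 / 92.2% | 17.1 / 10.9 / 3.7 |

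A normal-approximation check at d = 0.5 and r = 0.5 agrees. For the change score, 0.5/√(2/60) = 2.74 and Φ(2.74 − 1.96) = 0.78. With adjustment, 2.74/√0.75 = 3.16 and Φ(3.16 − 1.96) = 0.885. The unadjusted change score alone has power 64/78/94% at d = 0.5, so the rule recovers almost none of the gain.

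**4. Type I error under the rule.** 4.1%, 4.3% and 4.7% at r = 0.3, 0.5 and 0.7. There is no inflation.

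**5. Unequal SDs.** Let k be baseline SD divided by follow-up SD. The variance ratio becomes (1 − r²)/(1 + k² − 2kr). At k = 0.7:
- r = 0.3: 0.91/1.07 = 0.85, equivalent to 71 per arm
- r = 0.5: 0.75/0.79 = 0.95, equivalent to 63 per arm
- r = 0.7: 0.51/0.51 = 1.00, equivalent to 60 per arm

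The simulated gain falls to 5.5 / 1.2 / −0.1 points at d = 0.5 and 6.0 / 1.7 / −0.2 at d = 0.4.

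**6. If end-point scores were analysed instead.** With equal SDs the gain is 3.0 / 9.2 / 17.1 points at d = 0.5, 3.4 / 11.2 / 25.5 at d = 0.4 and 2.9 / 9.4 / 24.6 at d = 0.3.

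**The case against.** The strongest reply is that nothing here is an error. A change-score analysis of randomised arms is valid, type I error is controlled and the HAMD model already has its baseline term. That is correct, and it limits the point to precision and pre-specification.

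The second reply is that equal SDs flatter the gain. Entry requires a HAMD total of at least 21 (section 2.2), which may narrow the baseline spread of related scales while scores spread out as patients respond differently. The gain over a change score disappears when k = r. This stands: the smaller figures in step 5 are realistic, and the documents cannot say which case applies. Even then, adjustment costs at most about 0.2 points of power in the cases examined.

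Third, GLM is not defined. Section 3 lists week 0 among the time points, so a repeated-measures GLM with week 0 as a level would fit the text. The single-visit figures do not describe a model with several visits. With baseline and one follow-up visit, however, the arm-by-time test in that model is the change-score test, so the comparison still applies in kind.

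Fourth, the baseline phrase in the HAMD sentence might be meant to cover everything. It is attached to the drug-time interaction of that one model. If the wider meaning was intended, one sentence would settle it.

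Finally, the simulated rule assumes that baseline scores are among the variables tested. If they are not, the analysis is the plain change score, whose power is almost the same.

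**Conclusion.** The concern holds. For the GLMs on CGI, HAMA, BDI and SAS, the only stated criterion for a covariate is a significance test between randomised arms. That test admits a given baseline score in about 5% of trials regardless of its prognostic value.

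Pre-stated adjustment would gain about 2 to 17 points of power at 60 per arm if baseline and follow-up SDs are equal. It would gain about 6 points down to nothing if the baseline SD is 0.7 of the follow-up SD. All these figures rest on assumed effect sizes and correlations, one visit and change scores.

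There is no bias and no inflation of false positives. With complete data the HAMD drug-time interaction is not affected. This is a recommended improvement at almost no cost, not the repair of an invalid analysis.

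**What to change.** Before unblinding, delete the significance-based covariate rule from section 3 and replace it with wording such as:

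> Baseline characteristics will be summarised by arm; tests of baseline differences will not be used to choose covariates. Each GLM will be adjusted for the baseline value of the same measure where one is collected (baseline CGI-S for CGI-I; UKU has no baseline assessment in Table 1). Any further covariate will be pre-specified on prognostic grounds or reported as a labelled sensitivity analysis.

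The baseline term in the HAMD mixed model stays as it is. The deleted rule is worded for all analyses, so removing it also stops imbalance-driven covariates from entering that model. If a repeated-measures GLM is intended, the text should add that week 0 is a covariate and not one of the outcome time points.

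The cost is a few sentences and one degree of freedom per linear model. No extra patients, visits or data are needed.

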2.1 Overall Research Design

We will conduct a 48-week randomized, double-blind, placebo-controlled study to investigate the effects of adding fish oil to existing therapy for patients with MDD on: 1) reduce of clinical symptoms (measured by HAMD and CGI) 2) Cognitive improvement (measured by RANSE and STROOP); 3) Safety (UKU, BDI, SAS and clinical lab test) and 4) the biological indicator in blood serum, plasma and lymphocytes of patients between treatment groups and their correlation to clinical symptoms change.

The participators will take fish oil or placebo add-on to existing therapy for 24 weeks and the clinical symptoms, cognition, safety and blood samples will be assessed and collected before and after treatment (baseline, week 4, week 8, week 12, week 24 and week 48). The Evaluation scales used during the follow-up period are as follow:

HAMD (Hamilton depression scale);

HAMA (Hamilton anxiety scale);

CGI (Clinical global impression);

RBANS (Repeatable battery for the assessment of neuropsychological status);

STROOP (Stroop color-word test);
UKU (The UKU side effects rating scale);
CTQ (Childhood trauma questionnaire);
SSRS (Social support rating scale);
SAS (Self-rating anxiety scale);
BDI (Beck depression inventory);
ASEX (Arizona sexual experience scale);
HCL-32 (Hypomania Check List).

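### The primary HAMD outcome refers to 6 weeks, which is not a visit, and omits the scheduled week-8 rating; the secondary scales omit week 8 too

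*Combined protocol and SAP*

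**What the plan says.** Section 3 (Overall Approach to Statistical Analysis) gives the primary outcome as "Changes in Hamilton Depression Scale HAMD 6 weeks at week 0, week 4, week 12, week 24 and week 48 among study groups". The next sentence lists the same weeks, again without week 8, for the secondary scales CGI, HAMA, BDI and SAS.

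The rest of the document uses a different set of visits:

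- Summary: "Subjects will be assessed at baseline, week 4, week 8, week 12, week 24 and week 48".
- Section 2.1, for symptoms, cognition, safety and blood samples: "baseline, week 4, week 8, week 12, week 24 and week 48".
- Section 2.4: "Almost all clinical assessments will be done at baseline, week 4, week 8, week 12, week 24 and week 48", with an exception only for items done at baseline alone.
- Table 1: the row "HAMD, HAMA, CGI, BDI, SAS, RBANS, STROOP, ASEX, Somatic Self-rating Scale" is marked in all six columns, including W08.

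The analysis paragraph of section 3 compares the rate of HAMD improvement between arms. It uses a linear mixed model with subject as the random effect, a drug-by-time interaction and adjustment for baseline. It does not say which visits enter the model.

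**The concern.** The sentence that defines the primary outcome should settle which ratings count, and here it disagrees with the schedule in two ways: it refers to a time when nobody is assessed, and it leaves out a visit at which everybody should be. Nothing in the document explains either.

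Because the model paragraph names no visits, two analysts could fit different visit sets and each claim to follow the plan. One would use the five post-baseline ratings in Table 1, the other the four in section 3. That is avoidable freedom in the primary test.

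If the section 3 list is taken literally, a week-8 rating made during the capsule period plays no part in the primary outcome. A patient who leaves between weeks 8 and 12 would then contribute only week 4 after baseline, although a later rating exists.

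**Working it through.** The plan gives no power, effect size, standard deviation or dropout figure, so there is no stated number to reproduce. The check is a comparison of visit lists, a count, and a calculation of slope information.

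**Inputs.** Scheduled HAMD weeks: 0, 4, 8, 12, 24, 48 (section 2.4 and Table 1). Listed HAMD weeks: 0, 4, 12, 24, 48 (section 3). Sample size: 120, 60 per arm (section 2.2: "A total of 120 patients with MDD will be enrolled and randomly divided into 2 groups").

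**Step 1: compare the lists.** Week 6 is in neither list. The only scheduled week missing from section 3 is week 8.

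**Step 2: count post-baseline ratings, before dropout.**

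- Scheduled: 5 × 120 = 600.
- Listed: 4 × 120 = 480.
- Difference: 120, and 120/600 = 20%.

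**Step 3: slope information.** Assume complete data, a linear time effect, and independent residuals with variance σ² around a subject intercept. The variance of the difference in slopes is then 2σ²/(60 × Sxx), where Sxx = Σt² − (Σt)²/k over the k visit times. Section 3 does not make clear whether baseline is a response or only a covariate, so both cases are shown.

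| Visits in the model | Without week 8 | With week 8 | Ratio |
|---|---|---|---|
| Baseline as a response | 3040 − 88²/5 = 1491.2 | 3104 − 96²/6 = 1568.0 | 1.052 |
| Post-baseline only | 3040 − 88²/4 = 1104.0 | 3104 − 96²/5 = 1260.8 | 1.142 |

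Including week 8 therefore adds 5.2% or 14.2% to Sxx. The standard error of the slope difference is larger without week 8 by √1.0515 − 1 = 2.5% or √1.1420 − 1 = 6.9%.

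**Step 4: sensitivity to slopes that vary between patients.** If slopes vary with standard deviation s, the variance is proportional to s² + σ²/Sxx, and the gain shrinks. These values are assumptions, since the documents give none. With baseline as a response, the variance without week 8 divided by that with it is 1.026 for s = 0.1, σ = 4; 1.010 for s = 0.2, σ = 4; and 1.036 for s = 0.1, σ = 6. The 5% to 14% range thus applies to a model with a random intercept only.

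**The case against.** The strongest reply is that this is a drafting slip with little effect. The section 3 sentence can be read as listing reporting times, and the model paragraph does not exclude week 8. The listed weeks match the Table 1 row "Lab test and blood sample stored", which has no W08 mark, so the list may have been carried over from the laboratory schedule. The words 6 weeks are garbled, and the actual weeks follow at once, so nobody would try to analyse a week-6 visit. Much of this stands. A carry-over is possible but cannot be shown, and a slip in the only sentence that sets the primary outcome's time points still needs correcting.

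Four stronger readings are tempting but not supported:

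- **That the week-8 data are discarded.** The ratings are still scheduled, and the model paragraph sets no visit list. They are outside the outcome as defined only if that list is followed.
- **That one fifth of the information is lost.** One fifth counts ratings. The loss of slope precision is much smaller, as shown above.
- **That the gain can be quoted for an average on-treatment effect.** This needs a correlation and a dropout rate that the documents do not give. It would also compare the mean of weeks 4, 12 and 24 with the mean of weeks 4, 8, 12 and 24, which are different quantities. The plan specifies neither.
- **That the correction requires week 24 as the primary time point.** This would replace the planned rate of improvement with a new estimand. The freedom that comes from listing several weeks without naming a primary one is a separate issue and would remain after the words 6 weeks were deleted.

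**Conclusion.** The inconsistency is certain and rests on the text alone. Section 3 refers to a time that is not a visit and omits week 8 for HAMD and for the four secondary scales, against every schedule in the document.

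Its statistical size is modest: if the list governs the analysis, the plan forgoes slope information on the scale of the 5% to 14% calculated above. The upper figure, with baseline as a covariate only, may be the closer match to a baseline-adjusted model. Dropout, correlated residuals or slopes that vary between patients would change these values. No sample-size figure is affected, because the plan contains none.

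The point should be corrected because it sits in the definition of the primary outcome and the repair is nearly free. It does not by itself threaten the validity of the trial.

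**What to change.** In section 3:

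1. Delete the words 6 weeks from the primary outcome.
2. Add week 8 to the visit lists of the primary outcome and of CGI, HAMA, BDI and SAS.
3. Add one sentence to the analysis paragraph, for example: All scheduled post-baseline HAMD ratings (weeks 4, 8, 12, 24 and 48) enter the linear mixed model.

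If week 8 was left out on purpose, the plan should say so and give the reason. Either way, this should be settled before unblinding.

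The cost is wording only. Table 1 already schedules the ratings, so no visit or procedure changes. Whether to name a single primary time point is a separate question and is not part of this correction.

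### The primary HAMD analysis fits one drug-by-time trend across weeks on and off capsules, names no primary visit and leaves the coding of time open, so a real week-24 benefit could be diluted if it fades after capsules stop.

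*Combined protocol and SAP*

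**What the plan says.** **Treatment period.** Section 2.1 states: "The participators will take fish oil or placebo add-on to existing therapy for 24 weeks". Section 2.3 describes dosing "at roughly the same time each day, and lasting for the first 6 months". Section 2.2 adds follow-up after the 24 weeks, and Table 1 shows no dispensing at week 24. Week 48 is therefore the only scheduled visit that follows a period off capsules.

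**Primary outcome.** Section 3 defines it as "Changes in Hamilton Depression Scale HAMD 6 weeks at week 0, week 4, week 12, week 24 and week 48". No visit is singled out.

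**Primary analysis.** Section 3 says "the difference in the rate of HAMD improvement of fish oil group will be compared with that of the placebo group", using a linear mixed model with subject as the random effect. The tested term is "the drug-time interaction, with adjustment for baseline values". This is preceded by "After transformation (if necessary to insure the improvement is linear", which names neither the variable to be transformed nor the function.

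**Other relevant text.** Section 3 sets the test level: "two-sided testing and a 5% level of significance are planned for all statistical tests". The only analysis item tied to a later phase is "time to relapse for the maintenance phase of the study among study groups". It follows the secondary outcomes, and the maintenance phase is not defined anywhere.

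**The concern.** The stated hypothesis is that add-on fish oil is superior to placebo in treating symptoms. One trend fitted across both periods does not answer a clear version of that question. It estimates neither the difference at the end of capsules nor the difference at week 48.

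Two analysts could follow section 3 faithfully and run different primary tests: a slope on weeks, a slope on a transformed time scale, or a joint test of categorical visits. Adjusting for baseline also leaves open whether week 0 is an outcome in the model or only a covariate. These choices give different answers when the between-arm difference changes course after week 24. The result would then depend on off-capsule behaviour and on a coding decision that could be made after the data are seen.

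**Working it through.** The documents give no power, effect size, SD or correlation, so there is no planned figure to reproduce. The visits, 60 per arm and the two-sided 5% level come from the documents. Everything else is labelled as assumed.

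**1. Weight of each visit in a slope on weeks (schedule only).** For weeks 0, 4, 12, 24 and 48 the mean is 17.6 and SSx = 17.6² + 13.6² + 5.6² + 6.4² + 30.4² = 1491.2.
- Week 48: 30.4²/1491.2 = 62%.
- Week 24: 6.4²/1491.2 = 2.7%.
- On log(week+1) the shares are 29% and 10%.

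**2. Share of the on-capsule slope recovered (assumes a linear build to week 24).** Take between-arm differences of 0, −0.5, −1.5 and −3 at weeks 0, 4, 12 and 24. The on-capsule slope is −3/24 = −0.125 per week. The all-visit slope is Σ(t − 17.6)·difference/1491.2. The first four visits contribute 6.8 + 8.4 − 19.2 = −4.0 to the sum.
- None retained at week 48: −4.0/1491.2 = −0.0027, ratio 2%.
- Half retained: (−4.0 − 30.4×1.5)/1491.2 = −0.0333, ratio 27%.
- All retained: (−4.0 − 30.4×3)/1491.2 = −0.0638, ratio 51%.

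These ratios do not depend on effect size, SD or correlation.

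**3. Power (illustration).** Assumed: SD 6, constant within-patient correlation 0.5, no dropout, 3 points at week 24.
- Slope on weeks: SE = √(2/60 × 36 × 0.5/1491.2) = 0.0201. Power in favour of fish oil = Φ(−1.96 − slope/SE).
- Baseline-adjusted week-24 contrast: SE = 6 × √0.75 × √(2/60) = 0.949. Power = Φ(3/0.949 − 1.96) = 88.5%, whatever happens later.
- Baseline-adjusted week-48 contrast, same SE: 35% with half retained, 88.5% with all retained.

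| Test | None retained | Half | All |
|---|---|---|---|
| Slope on weeks, linear build | 3% | 38% | 89% |
| Slope on weeks, build of 1/2/3 points at weeks 4/12/24 | 2% | 27% | 82% |
| Slope on log(week+1), 1/2/3 build | 23% | 62% | 91% |
| Joint 4-df categorical test, 1/2/3 build, any direction | 78% | 62% | 78% |
| Week-24 contrast | 88.5% | 88.5% | 88.5% |

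Range for the 1/2/3 build, slope on weeks (none/half/all) against the week-24 contrast, changing one input at a time:
- SD 8: 2/17/57% against 66%.
- Peak of 2 points: 2/14/48% against 56%.
- 48 per arm: 2/22/73% against 81%.
- Correlation 0.4: 2/23/74% against 85%.
- Correlation 0.6: 2/32/89% against 93%.

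**4. Sign of the slope under full fade.** With the 1/2/3 build the slope on weeks is (13.6 + 11.2 − 19.2)/1491.2 = +0.0038, an adverse sign. If baseline is only a covariate and the slope uses weeks 4 to 48, it is +0.0290, with a 24% chance of a significant adverse slope. On log time it stays negative (−0.310). Fish oil is never worse than placebo at any visit in these scenarios.

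**The case against.** **The dilution needs two things that the documents do not state:** time coded as linear weeks, and a benefit that fades. This is correct. The plan's wording about a rate and about linearity makes the slope the natural reading, but that is an inference. With categorical visits the joint test keeps about 62–78% power in the 1/2/3 illustration, though it yields no single treatment effect. If a gradual benefit is fully retained, the slope on weeks has 82–89% power and little is lost. A reader might infer that the primary test will miss a fish oil benefit. The documents do not support that, because they predict no fade.

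**The transformation clause may help.** It can: log time raises power from 27% to 62% at half retention. But no monotone time scale makes a difference that rises and then falls linear, and the choice of function is left open.

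**A 48-week question may be intended.** The title says 12 months, and section 2.1 describes a 48-week study of adding fish oil. The superiority hypothesis names no time point. A reader might infer that week 24 is the only proper primary visit; the text does not establish that. What stands is that the plan does not choose, and a single slope estimates neither difference.

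**Time to relapse may cover the later phase.** It is undefined and leaves the primary test unchanged.

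A reader might also take an adverse slope under full fade as evidence for placebo. It is not: it reflects only the shape of the curve, and the visit means would show this.

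**Conclusion.** The concern holds in conditional form. From the text alone, the primary HAMD analysis does not separate on-capsule from off-capsule time, names no primary visit and does not fix how time is coded. From the schedule alone, a slope on weeks is dominated by week 48 (62%, against 2.7% for week 24).

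The size of any loss rests on assumptions about time coding, the shape of the build, retention after week 24, SD and correlation. In the illustration, power falls to 2–3% under full fade and 27–38% at half retention, against 88.5% for a week-24 contrast. With full retention of a gradual benefit the gap is small or absent. Confidence is high on the missing separation and medium on the size of the loss. This should be fixed.

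**What to change.** Amend the protocol and analysis plan before unblinding:

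- Replace the single slope with a mixed model containing baseline HAMD, treatment, categorical visit (weeks 4, 8, 12, 24 and 48) and treatment-by-visit.
- Name one primary contrast. Use week 24 if the primary question is the on-capsule treatment effect, with week 48 as a separate secondary durability contrast. Use week 48 if the primary question is the 48-week effect of being assigned capsules.
- Do not choose a time transformation after seeing the data.
- Reconcile the primary visit list in section 3 with Table 1: the list contains a reference to six weeks that matches no scheduled visit, and it omits week 8.
- Reconcile the primary outcomes: the Brief Summary lists HAM-D24, HAMA, BDI and SAS, whereas section 3 makes HAMD the only primary outcome and the other three secondary.

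A named visit contrast is preferable to a slope restricted to weeks 0–24. If a 3-point benefit is already complete at week 4 and persists, that slope has 56% power in the illustration, against 88.5% for the week-24 contrast.

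**Cost.** No new visits or data are needed, because Table 1 already schedules HAMD at all these visits. The model has a few more parameters, and one of the two time points becomes secondary. If the benefit fully persists, a log-time slope would have been slightly more powerful (91% against 88.5%).
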